This study will use a within subject design with oxytocin vs. oxytocin-matching placebo and yohimbine vs. yohimbine-matching placebo. The cue reactivity (CR) (opioid craving induced by personalized opioid cues) will follow the physiological symptoms (triggered by yohimbine) to isolate the stress signal associated with opioid. Eligible participants will be randomized to use intranasal oxytocin or placebo spray under double-blind conditions for 7 days. On days 5 and 7, participants will complete a session in which they receive yohimbine and one in which they receive placebo, under double-blind conditions, with the order of these conditions randomized across participants. After a two-day wash-out period, participants will receive the opposite condition within the oxytocin group (oxytocin or placebo, counterbalanced) to be administered for 7 days. On days 14 and 16, participants will complete an additional two labs where they will receive yohimbine and yohimbine matched placebo (counterbalanced). In a follow-up visit, we will complete final assessments before concluding the study (**Figure 1**).

FIGURE 1 - Pharmacological interventions during the study

Drugs and Doses Participants will receive intranasal oxytocin (40 IU) and oxytocin-matched placebo twice a day for 14 days; there will be one week of oxytocin administration and one week of placebo administration with two days of washout between the two conditions. They will receive two oral doses of yohimbine (32.4 mg) and two oral doses of yohimbine-matched placebo in the laboratory sessions.

[name] already obtained the Investigational New Drug (IND: 135570) from FDA for this study (Appendix A).

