Visit 3 (Laboratory Session I) – Day 5 Participants will provide a urine sample (drug toxicology), and a one vial blood sample (β -endorphin, hormone levels). Participants will then complete a series of assessments (**Table 1**) and receive a single oral dose of yohimbine or yohimbine-matched placebo. Fifteen minutes later, participants will administer a dose of oxytocin or oxytocin-matched placebo (40 IU, 4 sprays per nostril), after 30 min the first sample of saliva (cortisol and oxytocin) will be collected and the cue-reactivity will begin (112). Cue-Reactivity (CR) Task will be administered in a similar manner to other published studies (72, 73) for individuals with OUD with cues selected based on patients' drug experience. To measure cue-induced opioid craving, participants will a view images of neutral stimuli and then of opioid drug use (24). Participants will rate their craving via drug visual analog scale (VAS) and the second sample of saliva cortisol will be collected (45 min later). Vital signs will be monitored during the entire procedure. Participants will then complete Post-Cue measures, will have their vital signs measured and conduct the last sample of saliva.

Visit 4 (Laboratory Session II) – Day 7 Participants will come back after two days. The procedure will be similar to Visit 3 but they will receive the opposite condition (yohimbine or yohimbine-matched placebo).

A two-day washout period will occur followed by initiation of the opposite intranasal medication condition (i.e. oxytocin and oxytocin-matched placebo) to be administered for one week starting at day 9.

Visit 5 (Laboratory Session III) – Day 14 Participants will complete the lab procedures as described in Visit 3 and 4, however, this time will be administered the opposite oxytocin condition (i.e. oxytocin or oxytocin-matched placebo). Participants will also receive yohimbine or yohimbine-matched placebo (counterbalanced).

Visit 6 (Laboratory Session IV) – Day 17 Participants will come back after two days. The procedures will be completed as described in Visits 3-5, but they will receive the opposite condition (yohimbine or yohimbine-matched placebo).

Visit 7 (follow-up) – Day 20 After three days, participants will come to the lab for the final assessments (Table 1).

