The ITT analysis was suitable for this crossover design ³ as the placebo condition was treated identically to the active drug condition (route, administration and laboratory procedures). Distributional characteristics of outcome measures were examined to evaluate similarity to the normal distribution. detailed descriptive analysis of demographics, substance use, and clinical characteristics. The cortisol had a kurtosis in excess of four; consequently, an outlier analysis was performed and a total of 5 outliers falling outside of ±3 interguartile range were Winsorized as recommended ⁴. Comparisons with these characteristics, in relation to enrolled versus completer status, were performed using *t*-tests to analyze continuous variables (age) and χ^2 for categorical variables (sex, race, medication status). Attrition rates between the screening visit and follow-up visit were examined descriptively to assess for potential bias. In addition, a logistic regression was performed to test for possible bias due to period (placebo first, then oxytocin and oxytocin first, then placebo) or medication carryover (placebo and oxytocin), as done in our prior cross-over trial ⁵. This study tested the feasibility of the combined study design, the safety and tolerability of IN oxytocin and yohimbine, and the potential value of testing IN oxytocin as adjunct therapy in an appropriately-powered larger RCT. In selecting a target sample size, we balanced power considerations and feasibility given the preliminary nature of this trial. Because of the within-subjects design, power to test the effects of the study drug was optimized for this modest sample size. For the safety and tolerability outcomes (primary) adverse events, difference was detected based on a

judgement concerning the minimal effect, which has clinical relevance in the management of patients. In a noninferiority trial, the exact sample size could not be fixed in advance because it depends upon the chosen stopping guidelines ⁶.

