Outcomes: Primary (craving) and secondary (safety and tolerability) outcomes were assessed in realtime in the laboratory. Seven-day oxytocin administration was compared to the oxytocin-matched placebo condition during the CR procedure, in which noradrenergic activation produced by yohimbine or yohimbinematched placebo condition (2X2 design) was measured. We used Generalized Linear Model (GLM) with modelbased estimator in the covariance matrix, with medication (oxytocin/placebo) and noradrenergic activation (yohimbine/placebo) as within-subject factors. The model was specified to evaluate the effect of drug (oxytocin/placebo) by noradrenergic (vohimbine/placebo) interaction, main effect of the drug, and main effect of noradrenergic activation. Craving was assessed using the DDQ with time coded as: t_0 =relaxation, t_1 =interaction with drug paraphernalia/opioid auditory cues and t_2 =opioid use video. Safety and tolerability were assessed using: SBP, DBP, HR (vital signs), HAM-A and STAI (anxiety). The STAI y1 (state) was included as an additional safety measure for anxiety to ensure participants were not experiencing acute symptoms of anxiety within the laboratory. The STAI y2 (trait) was inserted as a covariate in the model to control for baseline anxiety level, along with stress (PSS), HPA (cortisol), and noradrenergic response (α -amylase). Time at laboratory sessions was coded as: t_0 =baseline, t_{45min} =45-min after yohimbine administration, and t_{90min} =post cue-exposure to specifically evaluate the contribution of each laboratory procedure (vohimbine and CR). Withdrawal symptoms (COWS) and AEs were assessed at specific timepoints: t_0 =pre-laboratory and t_1 =post-laboratory procedures.

Other outcomes (safety and tolerability) were measured retrospectively during the one-week outpatient setting and included the: COWS (withdrawal), anxiety (HAM-A and STAI), stress (PSS), depression (HAM-D) and AEs. The other outcomes were analyzed using ANOVA test and the number of AEs via a χ^2 test. For missing data approach, we first categorized missing data as missing completely at random (MCAR), missing at random (MAR) or missing not at random (MNAR)⁷. Analysis with GLM (using all available pairs of data to model missing values with maximum likelihood estimation) was deemed suitable for our analyses because no systematic differences existed between participants with missing data and those with complete data (MCAR)⁸.

Missing data reporting ⁹

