- 1. Amount of missing data in the dataset:
 - a. Oxytocin condition: 10% did not receive either oxytocin or placebo condition (within subject, *n*=16; between subject, *n*=4)
 - b. Yohimbine condition: 11.12% did not receive yohimbine condition (yohimbine, *n*=14; placebo, *n*=16; no yohimbine, *n*=4):

- 2. Reason for missing:
 - a. Oxytocin condition: change from between subject to within subject design
 - b. Yohimbine condition: safety concerns due to past history of cardiovascular disease and/or current hypertension (*n*=3), stroke (*n*=1)

3. Consequences:

- a. *Oxytocin condition*: no differences between participants with and without missing values except there were no subject taking methadone in the subjects with missing values.
- b. *Yohimbine condition*: no differences between participants with and without missing values except there were cardiovascular concerns in the subjects with missing values.
- 4. *Method*: GLM with MNAR using all available pairs of data to model missing values with maximum likelihood estimation
- 5. Software: IBM SPSS Statistics for Windows, version 29 (IBM Corp., Armonk, NY, USA)

All statistical analyses were performed after participants had completed their follow-up visits and the study database had been locked. The results were presented using summary statistics: number of subjects (n); mean (M); standard deviation (SD) or frequency distributions (%) and effect size was reported as Cohen's d.

All statistical procedures were performed by IBM SPSS Statistics for Windows, version 29 (IBM Corp., Armonk, NY, USA), and GraphPad Prism (v.10) was used to generate figures (La Jolla, CA, USA). All statistical tests were two-tailed, and statistical significance was accepted if an alpha value p<.05 was obtained.

References

1. FDA. Changes or modifications during the conduct of a clinical investigation; final guidance for industry and CDRH staff. 20012001.

Schulz K, Altman D, Moher D. Consolidated Standards of Reporting Trials Group CONSORT
2010 Statement: Updated Guidelines for Reporting Parallel Group Randomised Trials. Bmj.
2010;340:c332.

4. Tukey JW. The future of data analysis. The annals of mathematical statistics. 1962;33(1):1-67.

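### No planned analysis uses yohimbine order or session number, so the standard errors for the oxytocin-by-yohimbine test are uncertain in a direction the documents do not let one determine

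*Protocol*

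**What the plan says.** There are two layers of order. The first is spray order: oxytocin or placebo in the first seven-day course, the other in the second. The second is yohimbine order: which of the two sessions in a course carries yohimbine.

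For the first course (days 5 and 7), the design paragraph of Protocol Part III.3 gives the two sessions "with the order of these conditions randomized across participants". For the second course it plans "an additional two labs where they will receive yohimbine and yohimbine matched placebo (counterbalanced". The Visit 4 paragraph says that at the second session of a course "they will receive the opposite condition (yohimbine or yohimbine-matched placebo", and Visit 6 follows the same pattern. The aims section (Part III.2) calls both pairs counterbalanced. Nowhere is it stated whether a participant's course-2 order repeats, reverses or is independent of the course-1 order.

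The SAP's Statistical analysis section plans one order check, a logistic regression to "test for possible bias due to period (placebo first, then oxytocin and oxytocin first, then placebo", together with spray carryover. Its Outcomes paragraph specifies a generalized linear model with a model-based covariance, to evaluate the drug-by-noradrenergic interaction, "main effect of the drug, and main effect of noradrenergic activation". The covariates are trait anxiety, perceived stress, cortisol and alpha-amylase. Time in that paragraph means points inside one session. The working correlation is not named.

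**The concern.** The two sessions of a course repeat the same cue task a few days apart and differ in days of prior spray. A shift in craving from the first to the second is plausible. In any one participant it falls directly on the yohimbine-minus-placebo difference.

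Randomising the order keeps the expected contrast right, but the shift still adds person-to-person spread to some contrasts and none to others. One pooled model-based error cannot follow that. Contrasts that carry the shift get intervals that are too narrow; the rest get intervals that are too wide.

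The contrasts affected include the interaction and the Aim 1 comparison (oxytocin versus placebo after yohimbine). A spray-period adjustment targets a different shift, the one between courses, and leaves this one in place.

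**Working it through.** **Inputs from the documents.** 16 participants had both spray conditions (SAP, Missing data reporting). There are four sessions, two per course. For the test level: "All statistical tests were two-tailed, and statistical significance was accepted if an alpha value p<.05 was obtained". The plan gives no other figure on this point.

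**Assumptions, because the documents are silent.** Second-session shift s of 0.5 or 1 within-person SD (residual SD set to 1), one craving value per session, exchangeable error, complete sessions, no drug effects.

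**Where the shift goes.** Let a = +1 if yohimbine is in the second session of course 1 and −1 if in the first; let b be the same for course 2. Up to a sign set by spray order, one participant's contrasts pick up:

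- interaction (difference of the two yohimbine-minus-placebo differences): s(a − b), with noise variance 4;
- Aim 1 (the two yohimbine sessions compared): s(a − b)/2, with noise variance 2;
- oxytocin main effect: 0, because each course holds one first and one second session.

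A shift between courses cancels in the interaction, so a spray-course term cannot repair it.

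**True against pooled variance.** The shift adds a within-person sum of squares of 4 × (s/2)² = s² over 3 degrees of freedom, so the pooled variance is about 1 + s²/3: 1.083 at s = 0.5 and 1.333 at s = 1. The true variance factors are:

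- interaction: 1 + s² (reversed), 1 + s²/2 (independent), 1 (repeated or fully balanced);
- Aim 1: 1 + s²/2, 1 + s²/4 and 1 respectively;
- oxytocin main effect: 1 throughout.

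With R = true/pooled, the false-positive rate is 2[1 − Φ(1.96/√R)]. The last column is a simulation check: n = 16, person effects, spray order split 8/8, first yohimbine order drawn at random except in the balanced case, 4,000 runs per setting, Monte Carlo SE about 0.3 points at a 5% rate.

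| Course-2 order | Test | s = 0.5: R, rate | s = 1: R, rate | Simulated, s = 0.5 / 1 |
|---|---|---|---|---|
| Reversed, not exactly balanced | Interaction | 1.25/1.083 = 1.154, 6.8% | 2/1.333 = 1.5, 11.0% | 6.2% / 11.2% |
| Reversed, not exactly balanced | Aim 1 | 1.125/1.083 = 1.038, 5.4% | 1.5/1.333 = 1.125, 6.5% | 5.7% / 6.5% |
| Independent | Interaction | 1.038, 5.4% | 1.125, 6.5% | 5.2% / 6.7% |
| Independent | Aim 1 | 1.0625/1.083 = 0.981, 4.8% | 1.25/1.333 = 0.938, 4.3% | 5.1% / 4.4% |
| Repeated or fully balanced | Interaction, Aim 1 | 1/1.083 = 0.923, 4.1% | 1/1.333 = 0.75, 2.4% | 3.8–4.3% / 2.2–2.8% |
| Any | Oxytocin main effect | 0.923, 4.1% | 0.75, 2.4% | 3.7–4.7% / 2.1–3.0% |

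With no shift, the simulated interaction rate is 4.4–5.1%, so the set-up returns the nominal level.

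**Remedies compared.** With reversed order, adding a spray-course term leaves the interaction at 6.2% and 11.3%. With session number (1–4, categorical) every test in every scheme lies between 4.5% and 5.6%.

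**Precision.** With reversed order and s = 1, the interaction estimate has sampling SD 0.707 without the session term and 0.520 with it; 0.707/0.520 = 1.36. With no shift, the mean SE under reversed order goes from 0.497 to 0.515; 0.515/0.497 = 1.04.

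**The case against.** The strongest reply is that counterbalanced usually means balanced across participants. If yohimbine order were exactly balanced within each spray order, the shift would cancel from the group contrasts and the test would err on the safe side. That is correct, and the table shows it. But exact balance is not stated. Course 1 is described as randomised. The SAP also reports four participants with only one spray condition and four without yohimbine, either of which can break balance. Even under exact balance, the standard errors are too wide, which costs power.

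It can also be said that the pooled-error result is an assumption, because the SAP names no working correlation. This stands. If each participant's interaction contrast is tested against its own error, the rate stays at about 4.6% to 5.7% under independent or reversed order, and the loss is precision only. The SAP does specify a model-based estimator, so the pooled case cannot be set aside.

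Third, no passage shows that habituation or longer exposure shifts craving, and the cues are personalised. This also stands: a shift is plausible, but its size is unknown. Finally, the SAP describes the trial as preliminary, which lowers the stakes without removing the omission.

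**Conclusion.** The omission is real and is worth correcting. On the stated assumptions, the interaction test's error rate runs from about 2% to about 11% according to an order scheme the documents do not give. The Aim 1 contrast runs from about 2% to 7%. The oxytocin main-effect test becomes conservative, at about 2–3% with a 1 SD shift.

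A reader might infer three stronger things, and the documents support none of them:

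- **That leaving out order roughly doubles the false-positive rate.** That needs reversed order in course 2, first order not exactly balanced, a shift near 1 SD and a pooled error, all together. Pooling three craving readings per session under exchangeable correlation could give higher rates (14.2% at 1 SD with independent order and 14 participants), but the SAP does not say that this is the error structure.
- **That the estimates are biased.** With randomised order the expected contrast is unaffected; the fault lies in the standard error and in lost precision.
- **That yohimbine order was randomised separately in each course.** The design paragraph says so only for the first.

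**What to change.** In the SAP's Outcomes paragraph, add session number (1–4, categorical, which also absorbs spray course) as a fixed effect in the craving model and in the laboratory safety models, and name the working correlation. In the Statistical analysis section, add yohimbine order to the order check, tabulate it by spray order, and state whether the course-2 order was repeated, reversed or independent. Participants re-enrolled for the opposite condition (Protocol, Visits A and B) need a stated rule for numbering their later sessions.

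No new data are needed; if the models have already been fitted, they need refitting. The term uses 3 degrees of freedom. With 16 participants and complete sessions (16 × 4 = 64), the residual degrees of freedom in a person-effects model fall from 64 − 16 − 3 = 45 to 42. If there is no session shift, the SE rises by about 4–5%, and possibly somewhat more with the incomplete sessions that the SAP reports.

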In this double-blind, placebo controlled, randomized trial, individuals with OUD (*N*=50) who are currently receiving treatment with buprenorphine/naloxone or methadone will be randomized to intranasal oxytocin (40 international units, IU) and oxytocin-matched placebo, administered twice/day for 7 days with a minimum of two days between the opposite condition (oxytocin or placebo). On days 5 and 7, and on days 14 and 16, participants will complete two counter-balanced sessions in which they receive yohimbine (32.4 mg) or yohimbine-matched placebo, and responses to opioid cues are assessed.

Aim 1: assess the effects of oxytocin on cue-induced opioid craving after yohimbine stress-induced. We hypothesize that opioid craving will be reduced in the oxytocin condition, compared to the oxytocin-matched placebo, after yohimbine stress induction.

Aim 2: assess whether baseline levels of stress affect the effects of oxytocin on cue-induced opioid craving after yohimbine-matched placebo. We hypothesize that after yohimbine-matched placebo administration, opioid craving will be reduced in the oxytocin condition only among individuals with higher levels of stress at baseline.

Aim 3: to assess the safety and tolerability of oxytocin and yohimbine in OUD individuals receiving buprenorphine/naloxone or methadone. Participants will complete a laboratory session that includes a battery of medical/physiological/psychological assessments to monitor adverse events.

Aim 4:

Exploratory Aims: we will examine the effect of oxytocin, as compared to placebo, on neuroendocrine fluctuations of salivary cortisol (three points area under the curve) and blood neurotensin, orexin and substance P by comparing hormones concentrations at baseline and after study medication and placebo administration (visit 3, 4, 5 and 6).

This research will be the first to assess the clinical efficacy of repeated oxytocin administration to prevent opioid stress-induced relapse. Considering the high comorbidity between OUD, anxiety disorder and PTSD, this proposal will pave the avenue for testing oxytocin as an adjunct opioid replacement therapy (ORT) for an as needed personalized pharmacotherapy for this population.

[figure not shown]

If your study ONLY involves the use of identifiable secondary data / biospecimens, including coded data from which you may be able to ascertain identity, skip to PART VI. Otherwise, please continue.

3. Materials, Methods and Analysis.

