Oxytocin: The oxytocin and oxytocin-matched placebo will be formulated at 5mg/0.1mL (5mg/spray) and dispensed as 10-mL nasal spray, twice a day (2 sprays per nostril) for 7 days (total daily dose: 40 international units, IU). Previous pilot studies have demonstrated that oxytocin administered either as single dose (73) or daily for two weeks (72) was well-tolerated in individuals with co-occurring opioid and cocaine disorder. The intranasal dose was chosen based on earlier work (102, 103) and previous studies (69, 104) have shown that 40 IU is well-tolerated in healthy populations with minimal to no side effects or adverse events. The administration period (7 days) is within the confines of an acceptable timeframe based on previous studies and ongoing oxytocin clinical trials (NCT: 02407340 and NCT: 02548728). A study conducted by the PI's mentor, [name] and his team (105), indicated that both intranasal and intravenous exogenous (labelled) oxytocin cross the blood brain barrier and reach the CSF in rhesus macagues (106). As most of the neurohypophysial hormones, oxytocin has very short half-life, however, the pharmacological effect of oxytocin may extend from the transient kinetic effects. Intranasal oxytocin has shown to blunt stress effects on hippocampal synaptic plasticity and memory in rats via acting on oxytocin receptors and regulating phosphorylated extracellular signal-regulated kinases (pERK)(107). As such, oxytocin may induce compensatory mechanisms regulating secretion of magnocellular neurons in the hypothalamus which are operant on other hormones (108).

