Intervention: standard care + oxytocin 40 IU intranasal, twice a day

6. Compensation / Reimbursement

Compensation schedule and amount is described below:

Visit 1 will take ~ 4 hours and participants will receive \$40 for the visit.

Visit 2 ~1 hour and participants will receive \$40 for the visit.

Visits 3, 4, 5 and 6 will take ~3 hours and participants will receive \$100/visit.

Visit 7 will take ~1 hour and participants will receive \$20 + a \$50 bonus for completing the study.

Total possible compensation is \$550. Participants will be compensated in cash or Clincard and for the sessions that they complete. The amount of compensation is based on the time spent in each session and based on other similar study conducted by the PI or [name] at Brown University. Participants will receive parking validation or RIPTA tickets (both ways) as reimbursement for travel cost.

Participants that have previously completed the study and are re-enrolled in the opposite medication condition counterbalanced, will receive an extra \$20 for Visits A and B both; these visits are for safety criteria and to ensure eligibility once again. A sum of \$590 compensation is possible for these individuals.

7. Potential Research Risks / Discomforts to Participants.

- 1) discomfort from answering questionnaire items,
- 2) issues associated with undue inducement,
- 3) issues associated with coercion,
- 4) side effects or drug interactions with oxytocin,
- 5) craving for opioids,
- 6) discomfort from opioid craving during cue reactivity, and
- 7) discomfort from the neuroendocrine activation produce by yohimbine.

Participants will be protected against any potential risks and will be closely monitored throughout the study.

- 1. Participants may experience some discomfort when answering questionnaires items, however we expect that the risks will be low. Based on past and current research by Drs. [name] and [name], participants have not had any discomfort or issues that have arisen from questionnaires.
- 2. The risk of breach of confidentiality is low and strict precautions will be taken to minimize the risk of breach of confidentiality. A Data Safety Monitoring Plan (DSMP) will be in place that follows Brown's IRB guidelines.
- 3. The risk of undue inducement is low. Monetary compensation for this study is commensurate with the amount of time and effort that is required for the study.

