- 5. To protect against or minimize any risk of side effects associated with oxytocin, yohimbine or any drug-drug interactions, potential risks will be judiciously outlined to participants and thorough screening procedures will be in place to minimize recruitment of those that might be at a higher risk of adverse events. The study physician ([name]) and the CADRE NP will carefully review all participant screens and the PI will evaluate the individual medication profile to minimize any risk association with the medication. The participants will be instructed on the proper administration of the medication and they will return the spray bottle at the last visit. The safety of oxytocin is supported by other work with intranasal oxytocin spray (102, 103). No adverse events or side-effects were reported during the studies. [name] contact information will be provided to participants so that participants can contact him between visits if necessary.
- 6. To protect against or minimize any discomfort from opioid withdrawal, participants will be closely monitored throughout the study. Opioid withdrawal will be assessed before each visit and since individuals with a COW > 0 will be excluded from the study at screening, we don't expect withdrawal from opioids to be severe. [name] and/or the CADRE NP will be accessible 24/7 during the study and participants will be instructed to call if they experience any withdrawal symptoms. Emergency medical services will be immediately called if a serious adverse event arises during the study. Opioid withdrawal symptoms can be uncomfortable but are not dangerous.
- 7. To protect against or minimize any discomfort from opioid craving during cue reactivity, participants will be closely monitored throughout the laboratory session. Buprenorphine/naloxone or methadone level will be assessed at visit 3 to ensure ORT compliance. Participants' vital signs (BP, HR and MAP) and opioid craving with behavioral assessments will be monitored during the entire session.
- 8. The safety of yohimbine (32.4mg), formulated by Bayview Pharmacy is administered below the therapeutic index to a dose considered unsafe (>100mg). Furthermore, yohimbine will be administered only once, during the laboratory session.

The protocol involves an intervention proposed as an adjunct therapy to the standard care. There are minimal risk for participants in their daily lives, however they may feel discomfort during the

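### The protocol states the home oxytocin dose in two ways that differ two-fold (40 or 80 IU per day), and its dates for the second course and the last session do not agree

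*Protocol*

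**What the plan says.** **Home dose.**

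- Protocol Part III, section 3, Oxytocin paragraph: "dispensed as 10-mL nasal spray, twice a day (2 sprays per nostril) for 7 days (total daily dose: 40 international units, IU"). The same sentence says the product "will be formulated at 5mg/0.1mL (5mg/spray").
- Protocol Part III, end of section 5, the line defining the intervention: "Intervention: standard care + oxytocin 40 IU intranasal, twice a day".
- Protocol Part III, section 3, Drugs and Doses: "Participants will receive intranasal oxytocin (40 IU) and oxytocin-matched placebo twice a day for 14 days". Section 2 also gives 40 IU in brackets, then says the spray is "administered twice/day for 7 days with a minimum of two days between the opposite condition". In both places the 40 IU stands apart from the frequency, so it can be read per dose or per day.
- Protocol Part III, section 3, Visit 3: "participants will administer a dose of oxytocin or oxytocin-matched placebo (40 IU, 4 sprays per nostril"). Visits 4 to 6 follow the same procedure. The text does not say whether this dose replaces or adds to that day's home doses.

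**Dates.** Sections 2 and 3 (opening paragraph) put the second pair of sessions on days 14 and 16. The visit schedule in section 3 starts the one-week second course on day 9 and puts Visit 5 on day 14. It labels Visit 6 day 17 while describing it as two days after the previous visit. It puts follow-up on day 20, described as three days later.

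**The concern.** A dose stated two ways, a factor of two apart, is wrong in at least one place, and it is the dose of the investigational drug. Safety and tolerability is Aim 3. The SAP (Outcomes) analyses withdrawal, anxiety, stress, depression and adverse events collected retrospectively over the outpatient week. Those results describe the home regimen, and the protocol does not let a reader say whether they apply to 40 or 80 IU per day. The tolerability support has the same gap: earlier studies "have shown that 40 IU is well-tolerated in healthy populations", without saying whether that is per dose or per day. Table 1 also requires medication accountability at Visits 3 to 6, but expected home use is 56 or 112 sprays per course depending on which statement is followed.

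The dates matter because both period 1 sessions fall within the home course. If the last period 2 session falls after home dosing has stopped, its recent exposure differs from that of the other sessions.

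**Working it through.** **Calibration.** Visit 3: 4 sprays x 2 nostrils = 8 sprays for 40 IU, so 40 / 8 = 5 IU per spray.

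**The Oxytocin paragraph's own figure.** 2 sprays x 2 nostrils x 5 IU = 20 IU per administration; x 2 per day = 40 IU per day. The stated daily total is reproduced, but only if each spray holds 5 IU. The printed mg is therefore a unit error.

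**The section 5 line.** 40 IU x 2 = 80 IU per day. This needs 40 / 5 = 8 sprays per administration, or 4 per nostril, against the 2 per nostril in the Oxytocin paragraph.

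**Home dosing per 7-day course.** 40 x 7 = 280 IU (8 x 7 = 56 sprays) against 80 x 7 = 560 IU (16 x 7 = 112 sprays).

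**Allowing for the two laboratory doses per course.** How they relate to home doses is not stated, so each row is an assumption.

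| Laboratory dose | At 40 IU/day | At 80 IU/day | Gap |
|---|---|---|---|
| replaces both home doses that day | 5 x 40 + 2 x 40 = 280 IU | 5 x 80 + 2 x 40 = 480 IU | 200 IU |
| replaces one | 12 x 20 + 2 x 40 = 320 IU | 12 x 40 + 2 x 40 = 560 IU | 240 IU |
| is added | 280 + 80 = 360 IU | 560 + 80 = 640 IU | 280 IU |

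**Dates.** Course 1 runs from day 1 to day 7, with sessions on course days 5 and 7. Course day = session day - start day + 1; last course day = start day + 6.

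| Course 2 start | Course days | Day 14 | Day 16 | Day 17 |
|---|---|---|---|---|
| Day 9 | 9-15 | course day 6 | 1 day after | 2 days after |
| Day 10 | 10-16 | course day 5 | course day 7 | 1 day after |

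The table counts whole days. If course 2 began with one evening dose on day 9, its 14 administrations run 1 (day 9) + 6 x 2 (days 10-15) + 1 = 14. The last is then on the morning of day 16, so day 16 is reached but day 17 is not.

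**Visit spacing.** Visit 5 to Visit 6: 14 + 2 = 16, whereas 17 - 14 = 3. Visit 6 to follow-up: 20 - 17 = 3, whereas 20 - 16 = 4. The visit schedule therefore supports day 16 by one interval and day 17 by the other.

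**The case against.** The strongest reply on dose is that the Oxytocin paragraph is the dedicated dosing text. Its sprays, frequency and daily total agree with one another once the unit is corrected, and the only clear contrary statement is one summary line. That stands as far as it goes: sections 2 and 3 (Drugs and Doses) should not be counted as further statements of 80 IU per day. But the section 5 line defines the intervention and cannot be read as 40 IU per day.

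On dates, the reply is that day 9 and day 17 look like slips, since a day-10 start with sessions on days 14 and 16 reproduces period 1 exactly. This is plausible, but follow-up three days later on day 20 fits only day 17, so it remains an inference.

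Some stronger readings are tempting, and the documents do not support them:

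- **The last session follows the end of home dosing on either date.** This is certain only for day 17 (with a day-9 start, or a whole-day count from day 10). Day 16 is reached after an evening start on day 9.
- **The oxytocin-placebo contrast is biased.** The SAP measures craving and the main safety outcomes in the laboratory, where every session includes the supervised 40 IU dose. A uniform home dose does not bias the comparison. If both drug orders are balanced, the last session is spread evenly over the four drug cells.
- **The SAP's seven-day label is false for the last session.** The first session, on day 5, also precedes seven full days. The label describes the course length.
- **A day-9 start breaks the washout.** Only if two full drug-free days are meant. The protocol counts day 5 to day 7 as two days, and day 7 to day 9 is two days on that count.
- **The 10-mL bottle settles the dose.** At 0.1 mL per spray it holds 100 sprays, enough for 56 but not 112. If the laboratory doses replace both home doses and come from the same bottle, 80 IU per day needs 480 / 5 = 96 sprays and fits. Section 7 says participants use a bottle and "they will return the spray bottle at the last visit", but no number of bottles per course is given.

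**Conclusion.** The dose conflict is real and two-fold: 40 against 80 IU per day, or 280 against 560 IU of home dosing per course. Under the three assumptions about laboratory days, the gap in total course exposure is 200 to 280 IU. The mg per spray is an error of unit. The visit schedule also contradicts sections 2 and 3, and itself, on the date of the last session; a one-week course from day 9 cannot cover day 17.

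The consequence is limited. The primary laboratory contrast is not expected to be biased, given the supervised dose at each session and assuming balanced orders. What is affected is the dose label on the outpatient safety and tolerability results, and the comparability of home-dosing exposure at one of four sessions. At most 16 participants are concerned, the number the SAP (Missing data reporting) lists as within subject. The true number may be smaller, because earlier completers who re-enrolled through Visit A entered Visits 5 and 6 by a different route.

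Figure 1 and the drug attachments may state the intended regimen but are not available here. Even if they do, the two protocol statements cannot both be right, and which one is correct is for the sponsor to determine.

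**What to change.** The SAP places the trial in 2019-2023, so re-dating the course or extending home dosing can no longer change conduct. What remains useful:

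1. From dispensing and visit records, establish and report the home dose per administration and per day, how the laboratory dose related to that day's home doses, and the course day of each laboratory session.
2. In protocol Part III, sections 2, 3 (Drugs and Doses; Oxytocin) and the intervention line ending section 5, state one home dose with matching sprays per nostril, IU per spray and daily total. Change mg to IU if the records confirm it.
3. In Visit 3, state the laboratory-day rule.
4. Make the day-9 start, the day-16 or day-17 session and the day-20 follow-up agree across sections 2 and 3, and say whether washout means full drug-free days. If day 16 is right, follow-up three days later is day 19. If the records show a day-10 start, days 14 and 16 match period 1.

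The cost is text corrections in a handful of places and a check of existing records. No new data and no change to the analysis model are needed.
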